5.4.2 FACIT-Fatique

The questionnaire is a 13-item questionnaire that assesses self-reported fatigue and its impact upon daily activities and function.

Patients respond to each item on a 5-point Likert-type scale:

- 0 = not at all
- 1 = a little bit
- 2 = somewhat
- 3 =quite a bit
- 4 = very much

based on their experience of fatigue during the past 2 weeks.

The scale score is computed by summing the item scores, after reversing those items that are worded in the negative direction. It should be noted that numbering the questions from 1 to 13, it is evident that questions 7 and 8 are worded in the positive direction (4 indicates a desirable response) and all other questions are worded in the negative directions (4 indicates an undesirable response). Thus, it is necessary to reverse the responses for all but questions 7 and 8 (i.e. original response of 0 gets mapped to 4, 1=3, 2=2, 3=1, and 4=0) for scoring purposes. When there are missing item scores, the subscale score was computed by summing the non-missing item scores, multiplying by 13 (the total number of items in the scale) and dividing by the number of non-missing items (i.e. normalizing the results). The latter rule applied only when at least half of the items (seven or more) are non-missing.

FACIT-Fatigue subscale scores range from 0 to 52, where higher scores represent less fatigue.

5.4.3 SF-36

The Standard SF-36 v2 survey is used to measure health-related quality of life among healthy patients and patients with acute and chronic conditions. It consists of eight scales that can be scored individually (Maruish 2011). Note: Self-Evaluated Transition is not regarded as a scale.

Table 5-1 SF-36 domains

Domain	Total no. of items	Item
Physical Functioning	10	3a, 3b, 3c, 3d, 3e, 3f, 3g, 3h, 3i, 3j
Role-Physical	4	4a, 4b, 4c, 4d
Bodily Pain	2	7, 8
General Health	5	1, 11a, 11b, 11c, 11d
Vitality	4	9a, 9e, 9g, 9i
Social Functioning	2	6, 10
Role-Emotional	3	5a, 5b, 5c
Mental Health	5	9b, 9c, 9d, 9f, 9h
Self-Evaluated Transition	1	2

Each item will have a precoded item value as outlined in the table below.

Table 5-2 Precoded item values

Domain	Item	Response Choice	Precoded value
Physical Functioning	3a, 3b, 3c, 3d, 3e, 3f, 3g,	Yes, limited a lot	1
	3h, 3i, 3j	Yes, limited a little	2
		No, not limited at all	3
Role-	4a, 4b, 4c, 4d	All of the time	1
Physical		Most of the time	2
		Some of the time	3
		A little of the time	4
		None of the time	5
Bodily Pain	7	None	1
•		Very mild	2
		Mild	3
		Moderate	4
		Severe	5
		Very severe	6
		,	
	8 (if both Items 7 and 8 are answered)	Not at all (and Item 7 Precoded value=1)	1
		Not at all (and Item 7 Precoded value=2 through 6)	1
		A little bit (and Item 7 Precoded value=1 through 6)	2
		Moderately (and Item 7 Precoded value=1 through 6)	3
		Quite a bit (and Item 7 Precoded value=1 through 6)	4
		Extremely (and Item 7 Precoded value=1 through 6)	5
	9 (if Itom 7 is not	Not at all	1
	8 (if Item 7 is not answered)	Not at all A little bit	2
	,	Moderately	3
		Quite a bit	4
		Extremely	5
		LAGOTTOTY	
General	1	Excellent	1
Health		Very good	2
		Good	3
		Fair	4
		Poor	5

Domain	Item	Response Choice	Precoded value
	11a, 11c	Definitely True	1
		Mostly True	2
		Don't Know	3
		Mostly False	4
		Definitely False	5
	445 444	Definitely Two	1
	11b, 11d	Definitely True	
		Mostly True	2
		Don't Know	3
		Mostly False	4
		Definitely False	5
Vitality	9a, 9e	All of the time	1
	0, 0.0	Most of the time	2
		Some of the time	3
		A little of the time	4
		None of the time	5
		Note of the time	
	9g, 9i	All of the time	1
		Most of the time	2
		Some of the time	3
		A little of the time	4
		None of the time	5
Social Functioning	6	Not at all	1
r unclioning		Slightly	2
		Moderately	3
		Quite a bit	4
		Extremely	5
	10	All of the time	1
		Most of the time	2
		Some of the time	3
		A little of the time	4
		None of the time	5
Role-	5a, 5b, 5c	All of the time	1
Emotional	Ja, Jb, JC	Most of the time	2
EIIIOIIOIIAI		Some of the time	3

Domain	Item	Response Choice	Precoded value
		A little of the time	4
		None of the time	5
Mental	9b, 9c, 9f	All of the time	1
Health		Most of the time	2
		Some of the time	3
		A little of the time	4
		None of the time	5
	9d, 9h	All of the time	1
		Most of the time	2
		Some of the time	3
		A little of the time	4
		None of the time	5
Self-	2	Much better now than one year ago	1
Evaluated		Somewhat better now than one year ago	2
Transition		About the same as one year ago	3
		Somewhat worse now than one year ago	4
		Much worse now than one year ago	5

The source SF-36 data will be provided to the third party vendor Quality Metric via a secure data exchange. The vendor will complete the required derivations and provide a dataset to the Novartis study team containing:

- the scale scores transformed to 0 to 100 scores for each domain
- norm-based scores for each domain
 Note: These are the scores normed to the US population to have a mean of 50 and standard deviation of 10
- component summary scores (PCS, MCS)

Novartis

5.5 Statistical models

Primary analysis

SAS Code for Bayesian Analysis

The Bayesian analysis will be performed using SAS.

Note that for this illustrative example:

- the data are stored in the file data_set
- response1 = number of patients in the secukinumab treatment group who fulfil the primary endpoint

- number1 = number of patients in the secukinumab treatment group in the population of interest
- a1, b1 = the shape parameters from the prior Beta distribution [Beta(a,b)] associated with the secukinumab treatment group
- response2 = number of patients in the placebo treatment group who fulfil the primary endpoint
- number 2 = number of patients in the placebo treatment group in the population of interest
- a2, b2 = the shape parameters from the prior Beta distribution [Beta(a,b)] associated with the placebo treatment group

```
data <data set>;
*** set the seed;
call streaminit(190207);
  *** one hundred thousand draws from the Beta posterior distributions;
  do draw=1 to 100000;
    ***secukinumb treatment group;
   post resp1=RAND('BETA', <a1>+<response1>, <number1>+<b1><response1>);
    ***placebo treatment group;
   post resp2=RAND('BETA', <a2>+<response2>, <number2>+<b2>-<response2>);
    ***risk difference;
   rd=post resp1 - post resp2;
    ***risk ratio;
   rr=post resp1/post resp2;
    ***odds ratio;
    or=(post resp1/(1 - post resp1))/(post resp2/(1 - post resp2));
  end;
run;
***obtain percentiles of interest to determine median and 95%
credibility interval;
proc univariate data=<data set>;
  var post resp1 post resp2 rd rr or;
  output out=percentiles1 pctlpts=2.5 25 50 75 97.5 pctlpre=post1
post2 rd rr_ or_;
run;
***determine probabilities of interest;
proc sql;
 create table prob1 as
  select mean(or gt 1) as probnor1,
         mean(rd gt 0.22) as probnrd1,
         mean(rd gt 0.38) as probnrd2,
         mean(rd gt 0) as probnrd3,
         mean(rr gt 1) as probnrr1
  from <data set>;
quit;
```

Secondary analysis

SAS Code for Kaplan-Meier Plot

Novartis
SAP Amendment 1

The time to event analysis will be performed using the SAS procedure PROC LIFETEST.

Note that for this illustrative example:

- the data are stored in the file data set
- timevar = survival time
- censorvar = censoring variable (Note: 1 indicates a censored time)
- stratavar = stratification variable

```
ODS GRAPHICS ON;

PROC LIFETEST DATA=<data_set> PLOTS=survival (failure test at risk(outside(0.15))=0 to 360 by 30);

TIME <timevar> * <censorvar> (1);

STRATA <stratavar>;

RUN;
```

The option OUTSIDE(0.15) reserves 15% of the vertical graph window for the at-risk table. It can be adjusted.

SAS Codes for Kaplan-Meier Table

The summary statistics for time to event analysis will be performed using SAS procedure PROC LIFETEST.

Note that for this illustrative example:

- the data are stored in the file data set
- timevar = survival time
- censorvar = censoring variable (Note: 1 indicates a censored time)
- stratavar = stratification variable

SAS code for logistic regression

For the appropriate treatment difference, the treatment cohorts should be sorted or coded appropriately before using this model.

The analysis will be performed using SAS procedure PROC GENMOD as below. Note that for this illustrative example:

- the data are stored in the file data set
- treatmentvar = treatment cohort variable
- responsevar = dependent variable
- catvar = categorical variable of interest

• contvar = continuous variable of interest

```
PROC GENMOD DATA = <data_set>;
CLASS <treatmentvar> <catvar>
TABLES <responsevar> = <treatmentvar> <catvar> <contvar> / DIST=BINOMIAL
LINK=LOGIT;
LSMEANS <treatmentvar> / PDIFF CL;
RUN;
```

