2.5.2 Statistical hypothesis, model, and method of analysis

The primary endpoint variable of interest is binary, hence a binomial distribution will be assumed for the observed data from this study. It is of interest to estimate a one-dimensional scalar parameter (the primary endpoint estimand Θ) using Bayesian inference.

To perform this inference, a prior distribution for Θ must first be specified. The response rate of the comparable placebo arm of the GIACTA study (Stone et al 2017) will be used as the prior distribution for the placebo response rate for the primary endpoint in this study. The parameters of this Beta distribution are 10 and 43, i.e. Beta (10, 43). The prior distribution for the response rate on secukinumab will be a Beta distribution with parameters 0.5 and 0.5, i.e. Beta (0.5, 0.5). This prior distribution was chosen because it has low weight to reflect the lack of current knowledge on the response rate on secukinumab in GCA.

The process of Bayesian inference involves passing from a prior distribution, $p(\Theta)$, to a posterior distribution, $p(\Theta|y)$ where y refers to the data of interest from this study. Due to the conjugate nature of the Beta distributions, the posterior distributions of the primary endpoint

estimand Θ will also be Beta distributions. As the Beta distribution has a closed form nature, descriptive statistics of the posterior distribution are also available in closed form.

Using the prior distribution information and the study data, the Beta posterior distribution for each treatment group will be derived.

$$\Theta|y \sim Beta(y + a, n - y + b)$$

Note: y = study data (i.e. proportion of GCA patients who are in sustained remission until Week 28) for the treatment of interest; n = number of randomized patients for the treatment of interest; a, b = the shape parameters from the prior Beta distribution [Beta(a,b)] associated with the treatment of interest.

One hundred thousand random draws from the Beta posterior distributions will then be taken based on the seed 190207. An estimate of the 95% posterior interval (i.e. the 95% credibility interval), using the the 2.5 and 97.5 percentiles as well as the median (50 percentile) will be obtained. The median and 95% credibility interval of the OR, risk difference (RD) and risk ratio (RR) will be presented.

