Note: Odds ratio is the ratio of odds of the primary endpoint in secukinumab to the odds of the event in placebo. The odds of an event refers to the number of events / the number of non-events. Risk difference is the difference in proportions of the patients with the primary endpoint in secukinumab vs placebo. Risk ratio (also known as relative risk) is the ratio of risk of the primary endpoint in secukinumab to the risk of the primary endpoint in placebo.

For this study, similar response rates to the GIACTA study (Stone et al 2017) for the primary endpoint are expected, i.e. 56% secukinumab response rate and 18% placebo response rate. If the secukinumab response rate was < 40% this may indicate that further trials in this indication would not be worthwhile. Therefore assuming the 18% placebo response rate is fixed, the treatment response rates would translate into a RD of:

- 38% (expected effect, based on 56%-18%)
- 22% (minimal effect, based on 40%-18%)

This study would suggest to proceed with the development of secukinumab in this indication, if the following GO-criterium are satisfied:

• the posterior probability of a relevant effect (RD > 0.22) is at least 50% (also written as $prob(RD > 0.22 \mid y) \ge 50\%$)

and

• the posterior probability of any effect (RD > 0) is at least 90% (also written as prob(RD > 0 $|y| \ge 90\%$)

The posterior probabilities for a relevant effect and for any effect will be determined to give guidance in deciding whether to proceed in the development of secukinumab in this indication.

The posterior probability of the OR and the RR of the comparison of secukinumab versus placebo being greater than 1 will also be provided. Note: An OR or RR greater than 1 indicates a favourable outcome for secukinumab vs placebo in regard to the primary endpoint.

Furthermore, the proportion of patients in sustained remission until Week 28 (Yes, No) will be summarized descriptively by treatment group. This analysis does not take into account the prior information, it is only based on information from this study.

In addition, all primary endpoint data will be listed by treatment group, center, and subject number for the FAS.

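### The illustrative SAS program for the primary Bayesian analysis, as printed, stores one posterior draw rather than 100,000, so it does not implement the method in SAP 2.5.2

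*SAP*

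**What the plan says.** SAP 2.5.2 sets out the method: "One hundred thousand random draws from the Beta posterior distributions will then be taken based on the seed 190207". The 2.5, 50 and 97.5 percentiles of those draws give the median and the 95% credibility interval for the odds ratio, risk difference and risk ratio. The same section gives a two-part GO criterion. The first part is that "the posterior probability of a relevant effect (RD > 0.22) is at least 50" per cent; the second asks for a posterior probability of at least 90% that RD exceeds 0.

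SAP 5.5 supplies a SAS program for this analysis, introduced by "Note that for this illustrative example". Its DATA step sets the seed, opens the loop with "do draw=1 to 100000", draws one response rate per arm, and computes the risk difference, the risk ratio and finally the odds ratio: "or=(post resp1/(1 - post resp1))/(post resp2/(1 - post resp2" (closing brackets follow). The next statements are `end;` and `run;`. PROC UNIVARIATE then takes percentiles of the resulting data set, and PROC SQL takes the GO probabilities from it, for example "mean(rd gt 0.22) as probnrd1".

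**The concern.** The DATA step reads no input data set, and no OUTPUT statement is printed inside the loop. In SAS, each pass through the loop then overwrites the previous values, and one record is written when the step ends. The only other appearance of the keyword, "output out=percentiles1 pctlpts=2.5 25 50 75 97.5 pctlpre=post1", belongs to PROC UNIVARIATE. It saves percentiles and does not store draws.

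This is the only program the SAP gives for the primary estimate, its interval and the GO probabilities. If it were used unedited and unchecked, all of them would rest on a single random number. Because the seed is fixed, a rerun would repeat the same number, so repetition alone would not reveal the fault.

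**Working it through.** **Inputs.** Priors (SAP 2.5.2): Beta(0.5, 0.5) for secukinumab and Beta(10, 43) for placebo. Posterior for each arm: Beta(a + y, b + n − y). Planned size (SAP 3): n = 25 per arm, with 14 and 4 expected responders. GO requires P(RD>0.22) ≥ 0.50 and P(RD>0) ≥ 0.90.

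**Step 1: reproduce the plan's own figure.** SAP Table 3-1, first row (0.56 against 0.16), uses Beta(1, 1) for secukinumab, so the posteriors are Beta(1+14, 1+11) = Beta(15, 12) and Beta(10+4, 43+21) = Beta(14, 64). With 2,000,000 draws the 2.5%, 50% and 97.5% points of the difference are 0.170, 0.378 and 0.573, against 0.19, 0.38 and 0.56 in the table. P(p1>p2) is 0.9999 against 0.99. Over all six rows the quantiles agree within 0.02 and the medians within 0.01.

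**Step 2: the primary analysis with every draw kept.** At 14/25 against 4/25 the posteriors are Beta(14.5, 11.5) and Beta(14, 64). With 100,000 draws stored: RD median 0.38 (0.17 to 0.58), OR median 5.9 (2.3 to 16.3), RR median 3.1 (1.7 to 5.8), P(RD>0.22) = 0.93, P(RD>0) = 0.9998. GO is met.

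**Step 3: the program as printed.** SAS was not available, so the DATA step logic was emulated with another random number generator, keeping only the last pass. In one run at 14/25 against 4/25, a single record remained. RD was 0.098 and OR 1.61 at all three percentiles, with P(RD>0.22) = 0 and P(RD>0) = 1. SAS with seed 190207 would give a different draw but the same collapse.

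**Step 4: effect on the GO result.** With one record, the mean of an indicator is 0 or 1. If that draw exceeds 0.22 it also exceeds 0, so both criteria are met together; if not, the first fails. The chance of a reported GO therefore equals the true P(RD>0.22). Placebo is 4/25 throughout, and the last column comes from 3,000 seeds.

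| Secukinumab responders | Secukinumab posterior | Correct P(RD>0.22) | Correct P(RD>0) | Correct result | Share of seeds in which one draw gives GO |
|---|---|---|---|---|---|
| 8/25 | Beta(8.5, 17.5) | 0.23 | 0.93 | no GO | 0.23 |
| 9/25 | Beta(9.5, 16.5) | 0.36 | 0.97 | no GO | 0.36 |
| 10/25 | Beta(10.5, 15.5) | 0.51 | 0.99 | GO | 0.52 |
| 14/25 | Beta(14.5, 11.5) | 0.93 | 0.9998 | GO | 0.93 |

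Over the seeds, the reported P(RD>0.22) took only the values 0 and 1.

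**The case against.** The strongest reply is that SAP 2.5.2 governs and is correct. It states the draws, percentiles and thresholds without ambiguity. The program is labelled illustrative, is full of placeholders and cannot run until a programmer fills it in. An unedited run would also betray itself: one observation in the log, a zero-width interval, and every probability exactly 0 or 1. SAP 2.5.2 treats the GO probabilities as guidance, not as an automatic rule. All of this stands, and it limits the severity.

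A second reply is that the line may have been lost when the PDF was read. Characters clearly were lost in this block (underscores in variable names), and the code under the Kaplan-Meier table heading is absent altogether. A lost `output;` cannot be excluded. Against that, the loop text runs without a visible gap from the odds-ratio line to `end;`.

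Three stronger readings are tempting and are not supported:

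- **That the secukinumab posterior is misspecified.** The line "post resp1=RAND('BETA', <a1>+<response1>, <number1>+<b1><response1>" shows no minus sign before the responder count. SAP 2.5.2 gives the second shape parameter as n − y + b and the placebo line has the sign, so this is most likely a reading artefact.
- **That interim results are affected.** The interim analyses have their own SAPs, which are not in these documents, and nothing shows that they used this program.
- **That the planning figures are affected.** Table 3-1 shows intervals of ordinary width, so that simulation kept its draws. It was a separate calculation with 10,000 draws, so it does not show that the 5.5 program works either.

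**Conclusion.** The point holds for the program as printed: it keeps one draw and so does not implement SAP 2.5.2. The consequence is conditional on the code being run unedited and the output going unchecked. In that case the interval has zero width, and the GO result is wrong with a chance of about 23% at 8/25 against 4/25 and about 49% (1 − 0.51) at 10/25 against 4/25. These chances are over possible seeds; with the seed fixed, any given data set yields one fixed answer. They assume 25 patients per arm and the priors in SAP 2.5.2.

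A reader might infer that the primary analysis itself is invalid. The documents do not support that, because the specified method is sound and the fault lies in an example. This is a should-fix, subject to confirming that the source file also lacks the statement.

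**What to change.** First check the SAP source file, because of the extraction losses in this block. If the statement is missing there too, insert `output;` as the last statement before `end;` in the SAP 5.5 DATA step.

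Add two checks to the program specification:

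- The data set holds 100,000 records.
- The simulated medians of the two response rates, which PROC UNIVARIATE already reports, agree within Monte Carlo error with the exact medians of the two posterior Beta distributions, for example from the SAS QUANTILE function.

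The cost is one line of code and a short validation step. The method, priors, thresholds and sample size do not change.

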5.6 Rule of exclusion criteria of analysis sets

Table 5-4 Protocol deviation categories used

PD Category	PD Code
Eligibility	INCL or EXCL
Discontinuation of treatment/ study	WITH
Prohibited Concomitant Medication	COMD
Study drug (incorrect dose, wrong treatment)	TRT
Other	OTH

The full list of protocol deviations are defined in the edit check specifications which is located in the document management system in the following folder:

• 'CREDI Projects/A/AIN457A/CREDI Studies/AIN457ADE11C/Administrative Files (study level)/Validation and Planning documents'

Table 5-5 Patient classification

Analysis Set	PD ID that cause patients to be excluded	Non-PD criteria that cause patients to be excluded
RAS	OTH03	No informed consent;
FAS	OTH03	Not randomized No informed consent;
FAG	011103	Not randomized;
		No study drug taken during the study
Safety Set	OTH03	No informed consent;
		No study drug taken during the study

6 References

CAIN457 Project Master Analysis Plan (MAP)

- [CREDI Projects/A/AIN457A/Administrative files/CIS (Clinical Information Sciences)/Biostatistics AIN457 safety MAP M3 Amendment 5]
- [CREDI Projects/A/AIN457A/Administrative files/CIS (Clinical Information Sciences)/Biostatistics AIN457A efficacy MAP M3 Amendment 5]

CAIN457ADE11C Protocol

• [CREDI Projects/A/AIN457A/CREDI Studies/AIN457ADE11C/CSP (Clinical Study Protocol) – CAIN457ADE11C Protocol V02 Final 13052019 clean.pdf]

[Novartis (2020) COVID-19 (Coronavirus) Guidance Start and End Dates by Region for Sensitivity Analyses; Version 3.0 28-Oct-2020.]

Maruish, M. E. (Ed.). User's manual for the SF-36v2 Health Survey (3rd ed.). Lincoln, RI: QualityMetric Incorporated.

